### **6.3.2. Pharmacokinetics Population**

The PK Population will include all participants who received a complete dose of SAR440894 and have at least one quantifiable post-dose plasma drug concentration record.

### **6.3.3. Immunogenicity Population**

The Immunogenicity Population will include all participants who receive any amount of study product and contribute at least one post-infusion plasma sample for immunogenicity testing for which valid results are reported.

### **6.3.4. Pharmacokinetics – Immunogenicity Subset Population**

The Pharmacokinetics – Immunogenicity Subset Population will include all participants who received a complete dose of SAR440894, have sufficient data to permit estimation of PK parameters, and contribute at least one post-infusion plasma sample for immunogenicity testing for which valid results are reported.

## **6.4. Covariates and Subgroups**

The protocol does not define any formal subgroup analyses, and no formal subgroup analyses will be performed.

## **6.5. Missing Data**

All attempts will be made to collect all data per protocol. No imputation will be performed for missing values.

## **6.6. Interim Analyses and Data Monitoring**

Blinded combined safety data will be reviewed by the SRC after each cohort. Safety data may include, but is not limited to, vital signs, safety laboratory assessments, AEs, physical exam findings, and any noted trends through Day 14 for current cohort. The site PI(s) will also review the data in real time to assess whether any cohort dose escalation halting rules or study halting criteria have been met.

An ad hoc SMC meeting may be convened at any point throughout the study in response to a safety issue at the recommendation of the SRC.

## **6.7. Multicenter Studies**

Safety data will be presented according to whether participants enrolled prior to or under Protocol v11.0. For all participants enrolled prior to Protocol v11.0, AEs will be assessed by the investigator using a protocol-defined grading system (see [Table 4](#)) using the following categories: Mild (Grade 1), Moderate (Grade 2), and Severe (Grade 3). For participants who screen and enroll with Protocol Version 11.0, AEs will be assessed by the investigator using the NCI CTCAE, Version 5.0 – November 2017 [\[6\]](#) with the following categories: Grade 1 (Mild), Grade 2 (Moderate), Grade 3 (Severe), Grade 4 (Life-threatening), and Grade 5 (Death).

Likewise, clinical safety laboratory evaluations and vital signs will be assessed using a protocol-defined grading system provided in [Table 5](#) and [Table 6](#) for participants enrolled prior to Protocol v11.0. For

participants enrolled under Protocol v11.0, clinical safety laboratory evaluations and vital signs will be assessed by the investigator using the NCI CTCAE, Version 5.0 – November 2017 [6]. Additionally, prior to Protocol v11.0, all abnormal laboratory and vital signs findings were defined as AEs. However, with Protocol v11.0, the language was amended to state that only CS abnormal laboratory or vital signs findings will be defined as AEs. After discussion with DMID, for participants enrolled under Protocol v11.0, it was decided to also include related abnormal laboratory findings of any clinical significance as AEs. This will potentially result in differences in the number of clinical laboratory and vital signs AEs reported across treatment groups, depending on which protocol version the participant was enrolled under.

Given the timing of the finalization of Protocol v11.0, each site will adhere to only one of these toxicity grading methods for AEs, clinical laboratory evaluations, and vital signs. Safety data will otherwise be pooled across clinical sites.

All other data will be pooled across all clinical sites. Center effects are not otherwise anticipated because the sites are using standardized procedures for study product administration, and the study relies on central laboratories for the assessment of PK and immunogenicity endpoints.

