#### **3.2. Endpoints**

##### **3.2.1. Primary**

- Occurrence of adverse events (AEs) and serious adverse events (SAEs) following the start of study product administration through the final visit (Day 150 [ $\pm 7$ ]), or Early Termination (ET).
- The occurrence of clinically significant (CS) changes from baseline in vital signs and clinical safety laboratory values following administration of study product through final visit (Day 150 [ $\pm 7$ ]), or ET.
- The occurrence of CS changes in electrocardiogram (ECG) parameters post administration of study product through the final visit (Day 150 [ $\pm 7$ ]), or ET.

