## 9.7. Vital Signs and Physical Evaluations

Vital signs will include systolic blood pressure, diastolic blood pressure, heart rate, respiratory rate, and temperature. Vital signs will be assessed according to the schedule detailed in [Section 4.1](#) and [Table 2](#). Baseline will be defined for vital sign assessments according to the definition given in [Section 3.3](#). Clinical significance for post-baseline vital signs will be determined by the site PI with consideration to persistence, association with clinical symptoms, and impact to participant safety. For participants who screened and enrolled prior to Protocol v11.0, clinically significant vital signs will be determined by a blinded review from the site PI of all vital sign AEs reported. For participants who screened and enrolled with Protocol v11.0, clinically significant vital signs will include all abnormal vital signs results reported as AEs.

Toxicity grading criteria for vital signs results can be found in [Table 5](#) and [Table 6](#) for participants who screened and enrolled prior to Protocol v11.0. Vital signs results post-dosing for participants who screened and enrolled with Protocol v11.0 will be graded according to NCI CTCAE, Version 5.0 – November 2017. The distribution of vital signs results will be presented by severity, treatment group, and time point.

The sort order for vital signs assessments will be as follows: SBP, DBP, heart rate, respiratory rate, and temperature.

- Proportions of participants with mild, moderate, and severe results for any vital sign assessment will be presented for participants who enrolled prior to Protocol v11.0 in [Table 202](#) by treatment group, time point, and maximum severity. Proportions of participants with results that are mild, moderate, severe, life-threatening, or result in death for any vital sign assessment will be presented for participants who enrolled under Protocol v11.0 in [Table 203](#) by treatment group, time point, and maximum severity.
- Proportions of participants with graded abnormal vital signs results will be presented by treatment group, time point, and maximum severity separately for participants enrolled prior to Protocol v11.0 and for participants enrolled under Protocol v11.0 for vital sign parameters beginning in [Table 204](#) through [Table 213](#). Vital sign parameters with separate high and low toxicity ranges will be summarized by maximum severity for both high and low ranges.

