## **15. SUMMARY OF CHANGES IN THE CONDUCT OF THE STUDY OR PLANNED ANALYSES**

The following changes will be made in the final analysis:

- Protocol v11.0 states that creatinine clearance will be calculated and reported. However, in discussion with the study team, it was decided this parameter did not need to be included in the analysis and summaries, since eGFR is being collected and reported.
- Protocol v11.0 states that only CS abnormal laboratory findings will be reported as AEs. In discussion with the study team, it was decided related abnormal laboratory findings of any clinical significance will also be reported as AEs.

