## 14.3 Safety Data

### 14.3.1 Displays of Adverse Events

**Table 40: Overall Summary of Adverse Events – Participants in the Safety Population Enrolled Prior to Protocol v11.0**

	SAR440894 0.3 mg/kg (N = xx)		SAR440894 1 mg/kg (N = xx)		SAR440894 3 mg/kg (N = xx)		SAR440894 10 mg/kg (N = xx)		SAR440894 20 mg/kg (N = xx)		Placebo (N = xx)		All Participants (N = xx)	
Participants a with	n	%	n	%	n	%	n	%	n	%	n	%	n	%
At least one adverse event														
At least one related adverse event	x	x	x	x	x	x	x	x	x	x	x	x	x	x
Mild (Grade 1)	x	x	x	x	x	x	x	x	x	x	x	x	x	x
Moderate (Grade 2)														
Severe (Grade 3)	x	x	x	x	x	x	x	x	x	x	x	x	x	x
At least one severe (Grade 3) unsolicited adverse event														
Related	x	x	x	x	x	x	x	x	x	x	x	x	x	x
Unrelated	x	x	x	x	x	x	x	x	x	x	x	x	x	x
At least one serious adverse event	x	x	x	x	x	x	x	x	x	x	x	x	x	x
At least one related, serious adverse event	x	x	x	x	x	x	x	x	x	x	x	x	x	x
At least one adverse event leading to discontinuation of study product b														
At least one adverse event leading to early termination b														
At least one laboratory abnormality														
At least one related laboratory abnormality														
At least one clinically significant laboratory abnormality c														
Related														
Unrelated														
At least one not clinically significant laboratory abnormality c														
Related														
Unrelated														

Notes: N = Number of participants in the Safety Population

a Participants are counted once for each category regardless of the number of events.

b As reported on the Adverse Event eCRF.

c As reported on the Local Laboratory Results eCRFs.

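### No planned summary gives the any-AE rate under one rule, although which unrelated, non-significant laboratory findings and non-significant vital signs count as AEs depends on the protocol version at enrolment

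*SAP*

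**What the plan says.** SAP 3.2.1 states the first primary endpoint once, for all participants: "Occurrence of adverse events (AEs) and serious adverse events (SAEs) following the start of study product administration through the final visit" or early termination.

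SAP 6.7 then gives two rules for what counts. Of the earlier versions it says that "prior to Protocol v11.0, all abnormal laboratory and vital signs findings were defined as AEs". Of v11.0 it says that "only CS abnormal laboratory or vital signs findings will be defined as AEs", and that after discussion with the sponsor "it was decided to also include related abnormal laboratory findings of any clinical significance as AEs". SAP 15 repeats this addition. It covers laboratory findings only, not vital signs.

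SAP 6.7 itself warns that laboratory and vital-sign AE counts may differ between treatment groups for this reason. The response, in SAP 9.3 and 9.4, is to present AEs separately by version, with version-specific denominators.

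Some material for a common rule already exists. The Table 40 and 41 shells have rows such as "At least one not clinically significant laboratory abnormality", split into related and unrelated and taken from the local laboratory results eCRFs. For participants enrolled before v11.0, SAP 9.7 says that "clinically significant vital signs will be determined by a blinded review from the site PI of all vital sign AEs reported".

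**The concern.** A reader of the study report will look along the dose groups for the proportion with any AE. That proportion and its exact interval are the descriptive result for the first primary endpoint. If two doses enrolled under different versions, part of any difference between them may come from the counting rule and not from the product. Separate tables stop the two rules from being added together. They do not provide a figure that can be read across all five doses and placebo.

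Cohorts are dosed in ascending order (SAP 4.1), so version may overlap with dose. SAP 6.7 also says that each site uses only one grading method, so version is tied to site. SAP 3.3 says placebo is pooled, yet the AE tables divide it by version.

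**Working it through.** **1. The two rules side by side (SAP 6.7 and 15).**

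| Finding | Before v11.0 | Under v11.0 |
|---|---|---|
| Laboratory, clinically significant (CS) | AE | AE |
| Laboratory, not CS, related | AE | AE |
| Laboratory, not CS, not related | AE | not an AE |
| Vital sign, CS | AE | AE |
| Vital sign, not CS | AE | not an AE |
| Symptom or diagnosis | AE | AE |

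Two rows differ. The v11.0 rule is contained in the earlier one, so the earlier data can be cut down to it.

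**2. Where the two rows enter the displays.**

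- Tables 40/41: the any-AE row is affected. The laboratory-abnormality rows come from the laboratory eCRFs, so they do not depend on the AE rule.
- Tables 42/43: all TEAEs, so affected.
- Tables 44/45: the not-related and total columns are affected. The related column is the same for laboratory events; only a related, non-CS vital sign could differ.
- Tables 48 to 51 (SAEs, and AEs leading to discontinuation of product): incidental out-of-range values are unlikely to enter.
- Figures 13 to 16: related TEAEs only, so the laboratory rule is the same in both versions.

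**3. Can the one-rule rate be rebuilt from planned output?** Take laboratory findings alone. Suppose A participants in a group have any AE, and D of them have at least one laboratory AE that the v11.0 rule would drop. The number who keep at least one AE lies between A − D and A, depending on who also had another AE. Table 40 gives margins, not that overlap. The CS tables (120–123, 156–159, 171–172, 198–201, 219–220) are by parameter, so they do not give it either.

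**4. Effect of splitting placebo.** The planned size reproduces: 5 × (6 + 2) = 40, that is 30 active and 10 placebo. The version split is not given. Assume that k whole cohorts enrolled before v11.0. With zero events in n participants, the exact 95% upper limit is 1 − 0.025^(1/n).

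| k | Placebo before / under v11.0 | Upper limits |
|---|---|---|
| 1 | 2 / 8 | 84% / 37% |
| 2 | 4 / 6 | 60% / 46% |
| 3 | 6 / 4 | 46% / 60% |
| 4 | 8 / 2 | 37% / 84% |
| Pooled | 10 | 31% |

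**5. Size of the rule effect (illustration only).** SAP 4.5.1 lists 16 chemistry, 10 hematology, 3 coagulation and 10 urinalysis parameters, 39 in all. There are 10 scheduled post-dose laboratory visits, so m = 39 × 10 = 390 results per participant. This is a ceiling, because urine microscopy follows only an abnormal dipstick. Let q be the chance that a result is abnormal and s the share of abnormal results that are CS or related. Neither is in the documents. With independent results, the chance of at least one laboratory AE is 1 − (1 − q)^m under the earlier rule and 1 − (1 − qs)^m under v11.0.

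| q | Earlier rule | v11.0, s = 1% | v11.0, s = 20% | Gap (points) |
|---|---|---|---|---|
| 0.1% | 32.3% | 0.4% | 7.5% | 25 to 32 |
| 0.5% | 85.8% | 1.9% | 32.3% | 54 to 84 |
| 1% | 98.0% | 3.8% | 54.2% | 44 to 94 |
| 5% | about 100% | 17.7% | 98.0% | 2 to 82 |

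Repeated values in one person are correlated, so independence overstates the earlier-rule column. If instead only 10 to 29 effectively independent values each had a 5% chance of being out of range, the earlier-rule figure would be 1 − 0.95^10 = 40% to 1 − 0.95^29 = 77%.

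**The case against.** The case for leaving the plan alone has substance. The SAP is open about the change, and no planned AE table mixes the rules: within each table, every dose and its placebo share one definition. The analysis is descriptive with no hypothesis tests (SAP 6.8). CS laboratory and vital-sign results are tabulated for both versions, and the halting rules in Protocol 8.6 rest on related AEs or on SAEs. All of this stands, and it limits the point to the displays named above. It does not supply a one-rule any-AE rate.

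It is also true that a common rule cannot restore full comparability. Site, the investigator's judgement of significance and the grading scale still differ by version. That calls for a footnote; it is not a reason to omit the summary.

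A reader might infer three stronger things that the documents do not support:

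- **That AE rates are not comparable across doses at all.** Doses within one version share a rule, and related laboratory events are counted alike in both.
- **That higher doses will look safer.** Sequential dosing makes overlap with dose plausible, but the version-by-cohort split is not given.
- **That a particular bias can be quoted.** Any figure depends on abnormality and significance rates that are not in the documents. Several laboratory values were also exclusionary at screening, and many are graded in one direction only, so a plain 5% out-of-range rate is doubtful.

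**Conclusion.** The point holds in a limited form. Any-AE, not-related and total AE counts in Tables 40 to 45 should not be compared between doses enrolled under different protocol versions, and the plan offers no summary in which they can be. The difference comes from unrelated, non-CS laboratory findings and from non-CS vital signs.

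The size is unknown. The illustrative gap spans about 2 to 94 points, which shows only that it could be large and cannot be fixed in advance. The direction is unknown for the same reason as the split.

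The conclusion rests on SAP 6.7 for the earlier definition, because the earlier protocol versions are not among the documents. It would be harmless to keep the as-reported tables as the main display. The documents give no ground for demoting what investigators reported, so the addition should be supplementary.

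**What to change.** In SAP 9.3, keep the version-specific tables as they are and add one supplementary any-AE summary in the Table 40/42 format (n, %, exact interval). It should cover all participants by treatment group, with placebo pooled as SAP 3.3 intends, under the v11.0 rule as extended in SAP 15.

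- For participants enrolled before v11.0, exclude laboratory AEs recorded as both not clinically significant and not related.
- For the same participants, exclude vital-sign AEs judged not clinically significant in the SAP 9.7 blinded review.
- State how a laboratory AE is matched to its laboratory record. Protocol 8.5 keeps relationship, significance and grade on the laboratory form and says CS laboratory abnormalities are not entered as a separate AE eCRF. Reconcile that with SAP 6.7.
- Fix the rule before unblinding, and use this summary for any AE statement across versions.
- Report the number of participants by version, site and treatment group.
- Footnote that site, significance judgement and grading scale still differ by version.

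The cost is SAP wording, a derived flag and a repeat table. No new data and no protocol amendment are needed for the summary itself. The one downside is that pre-v11.0 counts in it may be lower than the as-reported counts, which the footnote should explain.

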## **6.8.     Multiple Comparisons/Multiplicity**

The analysis of the primary endpoint is descriptive and no formal hypothesis tests are planned for this study. Therefore, no adjustments for multiple testing are planned.

## 7. STUDY SUBJECTS

### 7.1. Disposition of Subjects

Screened participants who were ineligible for enrollment in the study (screen failures) or eligible but not enrolled will be summarized by inclusion and exclusion criteria ([Table 10](#)). Enrolled participants who were ineligible for inclusion in analysis populations will be summarized by reason for participant exclusion and treatment group ([Table 8](#)). Individual listings of participants who were excluded from the Safety Population, the PK Population, the Immunogenicity Population, or the Pharmacokinetics – Immunogenicity Subset Population will be listed ([Listing 5](#)).

Participant disposition will be summarized in [Table 7](#), displaying the number of participants who were screened, enrolled and randomized, received study product, had at least one quantifiable post-dosing plasma drug concentration measured, completed all planned PK blood draws, had at least one pre-infusion immunogenicity blood draw with valid results, had at least one post-infusion immunogenicity blood draw with valid results, completed all planned immunogenicity blood draws, completed final study visit, and terminated early. Participants who discontinued dosing or terminated early from the study will be listed ([Listing 2](#)). A flowchart displaying the disposition of study participants will be included ([Figure 2](#)). This figure will present the number of participants screened, enrolled, lost to follow-up, and analyzed by treatment group.

### 7.2. Protocol Deviations

A summary of participant-specific protocol deviations will be presented by the reason for the deviation, the deviation category, and treatment group for all participants ([Table 3](#)). This table will provide the number of participants and the number of deviations for each deviation and deviation type. All participant-specific protocol deviations and non-participant-specific protocol deviations will be listed in [Listing 3](#) and [Listing 4](#), respectively. All protocol deviations will be classified as either a major or minor deviation and summarized accordingly. As the question of a major or minor deviation wasn't included on the protocol deviation CRFs, the following process will be used to classify the deviations: (1) Prior to database lock, Emmes will generate a blinded spreadsheet of all protocol deviations and will assign major/minor according to the list in [Appendix 4](#); (2) DMID will review the list and confirm their agreement or not; (3) Once the classifications are completed and finalized, Emmes will incorporate this spreadsheet into their programming.

## **8. EFFICACY EVALUATION**

There are no efficacy endpoints for this trial.

## 9. SAFETY EVALUATION

### 9.1. Demographic and Other Baseline Characteristics

Summaries of sex, ethnicity, and race will be presented by treatment group (**Table 13**) and by site (**Table 11**). Ethnicity is categorized as Hispanic or Latino, or Not Hispanic or Latino, Unknown, or Not Reported. In accordance with NIH reporting policy, participants may self-designate as belonging to more than one race or may refuse to identify a race, the latter reflected in the CRF as “No” to each racial option. Summaries of age, height, weight, and body mass index (BMI) at Screening will be presented by treatment group (**Table 14**) and by site (**Table 12**).

Individual participant listings (**Appendix 3**) will be presented for all demographics and baseline characteristics (**Listing 6**).

#### 9.1.1. Prior and Concurrent Medical Conditions

All current illnesses and past pre-existing medical conditions will be coded using the Medical Dictionary for Regulatory Activities (MedDRA®) with MedDRA dictionary version 24.1 or higher. Summaries of participants’ pre-existing and concurrent medical conditions by MedDRA System Organ Class (SOC) will be presented by treatment group (**Table 15**). Individual participant listings will be presented for all pre-existing or concurrent medical conditions (**Listing 7**).

#### 9.1.2. Prior and Concomitant Medications

All medications will be coded to the Anatomical Therapeutic Classification (ATC) using the current version of the WHO Drug Dictionary. The use of concomitant medications taken during the study in the 45 days prior to study treatment administration through the last study visit will be summarized by treatment group, ATC 1, and ATC 2 (**Table 223**). Individual participant listings will be presented for all concomitant medications (**Listing 27**).

### 9.2. Measurements of Treatment Compliance

The dates of study product administration will be summarized by period and during the entire enrollment period in **Table 9** by site and treatment group. Date and time of study product administration, along with information on whether the participant was dosed according to protocol will be included in **Listing 8**. A listing of infusion interruptions will be presented in **Listing 9**.

### 9.3. Adverse Events

An AE that occurs during or after the first study product infusion and through the final visit is defined as a TEAE. Only TEAEs will be documented as AEs in this study. AEs will be presented separately for participants who enrolled prior to Protocol v11.0 and participants who enrolled under Protocol v11.0.

Overall summaries of TEAEs will be given in **Table 40** and **Table 41** for participants enrolled before Protocol v11.0 and for participants enrolled under Protocol v11.0, respectively. These tables will include the number of participants with at least one AE, number of participants with at least one related AE, number of participants with at least one SAE, and the number of participants with laboratory abnormalities.

All TEAEs will be presented for participants enrolled before Protocol v11.0 in **Listing 13** and for participants enrolled under Protocol v11.0 in **Listing 14**. Participant listings of non-serious AEs of moderate or greater severity will also be reported separately for participants enrolled prior to Protocol v11.0 (**Table 54**) and for

participants enrolled under Protocol v11.0 (**Table 55**). Individual listings of TEAEs leading to study product discontinuation will be presented for participants enrolled prior to Protocol v11.0 (**Table 56**) and for participants enrolled under Protocol v11.0 (**Table 57**).

The following summaries for TEAEs will be presented by treatment group, MedDRA System Organ Class (SOC), High Level Group Term (HLGT) and Preferred Term (PT):

- The number of TEAEs and number and proportion of participants reporting a TEAE will be presented for participants enrolled before Protocol v11.0 (**Table 42**) and for participants enrolled under Protocol v11.0 (**Table 43**). The exact Clopper-Pearson 95% CI for the proportion of participants experiencing each SOC/HLGT/PT will also be presented.
- The number and proportion of participants reporting a TEAE will be presented by treatment group, SOC, HLTG, PT, maximum severity, and relationship to study product for participants enrolled before Protocol v11.0 (**Table 44**) and for participants enrolled under Protocol v11.0 (**Table 45**). Participants will only be counted once per PT and highest severity but may be counted for any relationship to study treatment.
- The number and proportion of participants reporting a TEAE will also be presented by treatment group, SOC, HLTG, PT, and whether or not they resulted in alteration of administration of or discontinuation of study product for participants enrolled before Protocol v11.0 (**Table 46**) and for participants enrolled under Protocol v11.0 (**Table 47**).
- The number and proportion of participants reporting a TEAE leading to discontinuation of study product will be presented by treatment group, SOC, HLTG, PT, and relationship to study product for participants enrolled before Protocol v11.0 (**Table 50**) and for participants enrolled under Protocol v11.0 (**Table 51**). Participants will only be counted once per PT but may be counted for any relationship to study treatment.

Summaries of TEAEs will be presented graphically in bar charts by treatment group and SOC. For summaries of proportions of participants enrolled before Protocol v11.0 reporting a TEAE, denominators will be the number of participants in the Safety Population enrolled before Protocol v11.0 for each treatment group. For summaries of proportions of participants enrolled under Protocol v11.0 reporting a TEAE, denominators will be the number of participants in the Safety Population enrolled under Protocol v11.0 for each treatment group.

- The total number of related TEAEs reported will be presented by severity for participants enrolled before Protocol v11.0 (**Figure 13**) and for participants enrolled under Protocol v11.0 (**Figure 14**).
- The proportion of participants reporting a related TEAE will be presented by the maximum severity reported per SOC for participants enrolled before Protocol v11.0 (**Figure 15**) and for participants enrolled under Protocol v11.0 (**Figure 16**).

